1. OBJECTIVE

Specific Aims

Aim 1: ^{68}Ga -RM2 PET/MRI and ^{68}Ga PSMA-11 PET/MRI detection of PC. We will investigate the performance of the new GRPr-binding PET radiopharmaceutical, ^{68}Ga -RM2, and compare it to the currently most widely investigated (but not FDA-approved) PC PET radiopharmaceutical, ^{68}Ga PSMA-11, as well as to mpMRI acquired during PET/MRI for the localization and staging of low-risk and intermediate-risk PC. New lesions identified on PET/MRI and not known from prior systematic prostate biopsy will be confirmed by targeted biopsy and GRPr and PSMA status will be evaluated with specific immunohistochemical stains [1, 2].

Aim 2: ^{68}Ga -RM2 PET/MRI and ^{68}Ga PSMA-11 PET/MRI prediction of PFS after local targeted therapy for PC. We will investigate if the combination of the GRPr-binding PET imaging agent, ^{68}Ga -RM2, and the most widely investigated (but not FDA-approved) PSMA-binding PET imaging agent, ^{68}Ga PSMA-11, together with mpMRI can predict PFS after local targeted therapy. We will determine if ^{68}Ga -RM2 PET/MRI and ^{68}Ga -PSMA-11 PET/MRI assessment at 6-months follow-up will predict PFS at 24 months based on standard clinical follow-up (PSA, imaging, tissue diagnosis).

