Test to be evaluated: All T1w, T2w, DWI and DCE MR images will first be analyzed and graded by two-board certified abdominal radiologists with subspecialty training in body MRI and extensive clinical experience in prostate MRI (Drs. [name] and [name]), before and after treatment. Areas of focally increased ⁶⁸Ga-RM2 or ⁶⁸Ga-PSMA-11 uptake above surrounding background on pre-therapy scans will be evaluated for changes in uptake by Drs. [name] and [name].

Hypotheses

Primary: Change in ⁶⁸Ga-RM2 or ⁶⁸Ga-PSMA-11 uptake from baseline (T0) to 6 months after start of treatment (T1) will predict treatment response better than T0-T1 changes in MRI.

Secondary: T0-T1 change in ⁶⁸Ga-RM2 or ⁶⁸Ga-PSMA-11 uptake will predict progression-free survival (PFS) better than MRI.

Statistical Analysis:

Primary: (a) logistic regression of response/non-response at T6 on T1-T0 change in PET/MRI measures; (b) McNemar tests of MRI and PET predictions of T6 response.

Secondary: (a) log-rank tests of PFS time (length of drug response) on patients dichotomized as above/below the median change in PET/MRI measures; (b) Cox proportional-hazards regressions of PFS on amount of T1-T0 change in PET/MRI measures.

Statistical Power and Sample Size: We expect a 70-80% response rate to treatment, and 20% of responders progressing by two years.

A sample size of ~75 responders and ~25 non-responders will provide 90% power at one-sided 5% error to detect sensitivity low as 80% at fixed 90% specificity, and to demonstrate a difference in sensitivities of 10 percentage points (e.g., 80% vs 90%).

Median-change groups of ~40 each among the responders will provide 90% power at one-sided 5% error to detect differences in PFS hazard ratios as small as 2.5.

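### Section 10.2 contradicts itself on PFS: the log-rank gloss and its power line describe responders only, while the aim, population, hypothesis and Cox model cover all enrolled men

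*Combined protocol and SAP*

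**What the plan says.** Section 1 sets Aim 2 as "PET/MRI prediction of PFS after local targeted therapy for PC", judged at 24 months. Section 10.2 takes the Aim 2 participants to be the men enrolled in Aim 1. Its secondary hypothesis is that uptake change between baseline and 6 months predicts PFS better than MRI, with no limit to responders.

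The secondary analysis has two parts. Part (a) is "log-rank tests of PFS time (length of drug response) on patients dichotomized" above or below the median change. Part (b) is "Cox proportional-hazards regressions of PFS on amount of T1-T0 change in PET/MRI measures", with neither the gloss nor any restriction.

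The power text states: "We expect a 70-80% response rate to treatment, and 20% of responders progressing by two years". It then sizes the PFS comparison, for a hazard ratio of 2.5 or more: "Median-change groups of ~40 each among the responders will provide 90% power at one-sided 5% error". No progression rate is given for non-responders. PFS is said to rest on standard clinical follow-up, without a start date, event rule or censoring rule.

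**The concern.** Length of response is not PFS. It exists only for men who respond and starts at response. The wording also does not suit this trial, where the treatment is local therapy (HDR brachytherapy) and not a drug. The gloss, the group sizes and the only progression rate given all point to responders; the aim, participant set, hypothesis and Cox model point to everyone. Two analysts could follow Section 10.2 in good faith and test different variables in different populations.

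Response is also the outcome that uptake change is meant to forecast under the primary hypothesis of Aim 2. Restricting to responders therefore selects on something the predictor is expected to drive. That narrows the predictor's range and removes the men most likely to progress early. A useful marker could then look weak, and prediction of PFS at 24 months is part of a stated primary objective.

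**Working it through.** **1. The stated power.** Inputs from Section 10.2: hazard ratio 2.5, one-sided 5%, 90% power, two groups of about 40, and 20% of responders progressing by two years.

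- Events needed (Schoenfeld, 1:1) = 4(1.645 + 1.282)² / (ln 2.5)² = 34.27 / 0.840 = 40.8, so 41. Freedman's formula gives 47.
- Events expected = 20% of 70-80 responders = 14-16.
- Power = Φ(ln 2.5 × √events / 2 − 1.645). For 14 events: Φ(1.714 − 1.645) = 53%. For 16 events: Φ(1.833 − 1.645) = 57%.

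The 90% does not reproduce. It would need 41 of 80 responders (51%) to progress. Reading the 20% as the rate in the better median group only gives 25 events and 74%; in the worse group only, 11 events and 46%. With 16 events, the hazard ratio detectable at 90% power is about 4.3. Two groups of 40 also imply 80 responders, the top of the 70-80% range, although the preceding power statement uses about 75.

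**2. Who lies outside the sized comparison.** At a 70-80% response rate, 20-30 of 100 men.

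**3. Events in all men.** The non-responder progression rate q is not in the documents, so it is an assumption shown as a range. With 75 responders, events = 75 × 0.20 + 25q. Power is for hazard ratio 2.5, before any landmark.

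| q | Events | Power |
|---|---|---|
| 20% | 20 | 66% |
| 50% | 27.5 | 78% |
| 80% | 35 | 86% |
| 100% | 40 | 89.5% |

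The responder-only share is 15 events, so the loss is 12.5 of 27.5 (45%) at q = 50% and 25 of 40 (62.5%) at q = 100%.

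**4. Attenuation, as an illustration.** Assumed values, not in the documents: a latent residual-disease score drives both response and hazard; 75% respond; 20% of responders and 75% of non-responders progress by 24 months; uptake change correlates 0.5 with the score. Only men progression-free at month 6 are analysed, with time counted from month 6.

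| Set | Events per 100 enrolled | Median-split HR | Power |
|---|---|---|---|
| All men | about 21 | about 2.1 | about 50% |
| Responders only | about 11 | 1.5-1.6 | 17-20% |

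Without the landmark the all-men figure is about 34 events, but some 13 of these fall before month 6, when the predictor does not yet exist.

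**5. Does attenuation depend on the link to response?** A second simulation (75% respond; 20% and 80% progress; no landmark) varied that link.

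| Uptake change predicts | HR, all men | HR, responders |
|---|---|---|
| Response only, strongly (log-odds 2 per SD) | 2.5 | about 1.0 |
| Response (log-odds 1 per SD) and PFS (log-HR 0.6 per SD) | 3.5 | 2.5 |
| PFS only (log-HR 0.6 per SD) | 2.1 | 2.5 |

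The direction reverses when uptake change does not predict response.

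**The case against.** The strongest reply is that no rule excludes non-responders. The log-rank test is written for patients, the Cox model is unrestricted, Aim 2 takes everyone from Aim 1, and the restriction to responders appears only in the power sentence. On that view the gloss is a stray phrase. This stands in part. A reader might infer that a responder-only duration has replaced PFS and that non-responders drop out, but the documents do not say so. They do leave a contradiction that no definition resolves.

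Three other tempting inferences also go too far:

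- **Dilution is certain.** It depends on uptake change predicting response. That is the primary hypothesis, but the plan gives no strength for it, and step 5 shows the reverse without it.
- **Most events are lost.** That depends on the unstated non-responder rate; at 50% progression the loss is 45%.
- **Starting the clock at response distorts the test.** If response is judged at the same month for every man, this subtracts a constant from each responder's time and leaves log-rank and Cox results unchanged. The population is what matters.

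Moving to all men does not by itself rescue the power. In step 3 the 41 events are not reached at 75 responders even if every non-responder progresses, and the landmark lowers the count further.

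**Conclusion.** The point holds as an internal contradiction. Section 10.2 names one variable and population in the log-rank gloss and power line, and another in the hypothesis, participant set and Cox model. Followed literally, part (a) would test duration of response in a subset chosen on an outcome the predictor is meant to forecast.

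The size of the harm is conditional. It requires that the responder-only reading is applied and that uptake change predicts response. On the assumed values in step 4, the hazard ratio falls from about 2.1 to 1.5-1.6 and power from about 50% to 17-20%.

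The power shortfall needs no assumption about non-responders. On the plan's own figures, read as an overall 20% among responders, power is 53-57% against the stated 90%.

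**What to change.** In Section 10.2:

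1. Delete the parenthetical gloss on PFS time and the restriction to responders in the power line.
2. Define PFS as time from the 6-month scan (landmark) to first documented progression, censored at last follow-up. Include every treated man with a baseline-to-6-month change who is progression-free at that scan, whether or not he responded.
3. Use this one set for the median split, log-rank test and Cox model. Report men who progress before the landmark separately. Keep duration of response in responders as a labelled sensitivity analysis.
4. Restate the PFS power from expected events after the landmark, with an explicit assumed non-responder progression rate and its range, and withdraw the 90% unless the event count supports it.
5. Reconcile the chart-review period. Section 6.3 gives 12 months after the scan; footnote b of the Section 7 calendar gives 24 months from the initial scan, which precedes treatment. Neither clearly supplies 24 months from treatment, so the text should state the origin of the 24-month PFS claim and follow-up that reaches it.

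Items 1 to 4 cost SAP wording and one recalculation. They need no new scans, since the imaging and chart review are not limited to responders. Item 5 may require longer chart review, depending on how the two periods are reconciled.

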Because there may be multiple lesions per-patient and an indefinite number of non-lesions, the primary analysis will be per-region. Each of the 12 regions will have gold-standard positive or negative information, as well as imaging positive or negative assessments. Predictive accuracy of PI-RADS composite score (mpMRI) and SUV_{\max} PET uptake values will be assessed by ROC analysis using univariable logistic regression for the presence of PC. Areas under the entire ROC curve, and partial area at fixed 90% specificity will be compared. Additional benefit of the other modalities over mpMRI alone will be tested by a multivariable logistic regression. All analyses will be adjusted for clustering within patient.

Statistical Power and Sample Size: Based on our clinical experience at Stanford, we expect an average of 2 PC-positive regions and 10 PC-negative regions per patient. Assuming mpMRI has sensitivity of 80% and specificity of 80-90% [91], a sample size of 1200 regions with 20% prevalence will provide 90% power at 5% error to demonstrate non-inferiority of a PET sensitivity of 90% at 80-90% specificity [62, 92, 93].

The per-lesion analysis will depend on the number of lesions found but will be similar. We will also explore whether specific imaging findings are especially accurate in detection of specific subtypes of PC or prostate regions (i.e., peripheral versus transitional zones). It may also be the case that

predictive failures in imaging may be associated with a particular subtype. Given the small sample, we acknowledge that this analysis will be exploratory.

10.2 Aim 2

Participants: Those enrolled in Aim 1.

Design: Patients will be scanned with both ⁶⁸Ga-RM2 PET/MRI and ⁶⁸Ga-PSMA-11 PET/MRI at six months after initiation of therapy. MRI and PET images will each be evaluated separately.

Outcome measures: Changes in MRI features and/or changes in radiopharmaceutical uptake in lesions will be recorded for each modality in each patient. Gold standard of response to treatment and of PFS will be based on standard clinical follow-up (PSA, imaging, tissue diagnosis including IHC stains for GRPr and PSMA)

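### Aim 2: the stated 90% power for 80% versus 90% sensitivity with about 75 responders does not follow from its inputs; it needs near-complete nesting of MRI-correct within PET-correct men, which the plan does not state

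*Combined protocol and SAP*

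**What the plan says.** Section 10.2 (Aim 2) sets as primary hypothesis that the change in tracer uptake from baseline to six months "will predict treatment response better than T0-T1 changes in MRI". Two primary analyses are listed: (a) a logistic regression of response on the change, and (b) "McNemar tests of MRI and PET predictions of T6 response". Both modalities are assessed in the same patients; the design paragraph says that "MRI and PET images will each be evaluated separately".

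The power paragraph begins "We expect a 70-80% response rate to treatment, and 20% of responders progressing by two years". It then states that "A sample size of ~75 responders and ~25 non-responders will provide 90% power at one-sided 5% error", first for a sensitivity as low as 80% with specificity fixed at 90%, and then for a 10-percentage-point difference in sensitivities, with 80% against 90% as the example.

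The section gives no discordance or correlation between PET and MRI predictions, no form of the McNemar test (exact, mid-p, uncorrected or continuity-corrected) and no power formula. It does not say whether response or non-response is the positive class for sensitivity.

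**The concern.** A McNemar test uses only the men in whom PET and MRI disagree. For a fixed 10-point gap, power falls as the number of disagreements in both directions rises. A claim of 90% from sample size, error rate and two sensitivities alone therefore lacks an input, and the value it would need lies at the most favourable edge of what is possible.

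This is the only power statement for the primary hypothesis of Aim 2. If the real power is nearer one half to three quarters, a non-significant McNemar result would say little, yet a reader who trusted the stated 90% could take it as evidence that PET is no better than MRI.

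**Working it through.** **Inputs from section 10.2.** n = 75 responders; one-sided 5% error (z = 1.645); sensitivities 0.80 and 0.90, so d = 0.10; paired McNemar test.

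**Input not in the plan.** The discordant share ψ (PET right and MRI wrong, plus the reverse). Its possible range follows from the two sensitivities:
- Minimum 0.10: every man MRI gets right is also right on PET (complete nesting).
- Independent errors: 0.9×0.2 + 0.1×0.8 = 0.26.
- Maximum 0.30: no man is wrong on both (0.10 + 0.20).

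The range 0.10 to 0.26 is used below as an assumption, with 0.30 shown as the limit.

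**Formula.** Power = Φ[(d√n − 1.645√ψ) / √(ψ − d²)], with d√n = 0.10×8.660 = 0.866.
- ψ = 0.10: (0.866 − 0.520)/0.300 = 1.153, power 87.6%.
- ψ = 0.18: (0.866 − 0.698)/0.412 = 0.408, power 65.8%.
- ψ = 0.26: (0.866 − 0.839)/0.500 = 0.055, power 52.2%.

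**Attempt to reproduce 90%.** The formula does not reach it at n = 75. The Wald variance gives 89.3% at ψ = 0.10. Two independent groups of 75 give 52.8%. A one-sample test of 90% against 80% gives 75.6% (normal) or 66.6% (exact).

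**All variants at n = 75, one-sided 5%.** The second column is the expected number of men right on MRI and wrong on PET, 75×(ψ − 0.10)/2. The last three columns are by enumeration.

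| ψ | MRI-only right (men) | Formula | Exact | Mid-p | Uncorrected |
|---|---|---|---|---|---|
| 0.10 | 0 | 87.6% | 88.1% | 95.0% | 98.4% |
| 0.11 | 0.4 | 84.5% | 81.7% | 89.6% | 92.1% |
| 0.12 | 0.75 | 81.4% | 76.3% | 84.9% | 87.7% |
| 0.14 | 1.5 | 75.6% | 68.1% | 77.4% | 80.7% |
| 0.18 | 3 | 65.8% | 57.7% | 66.9% | 68.5% |
| 0.26 | 6 | 52.2% | 44.8% | 52.6% | 52.6% |
| 0.30 | 7.5 | 47.4% | 40.3% | 47.5% | 47.5% |

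**Responders needed for 90%.** n = [(1.645√ψ + 1.282√(ψ − d²))/d]² gives 82 at ψ = 0.10, 151 at 0.18 and 219 at 0.26.

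**Gap that 75 responders can detect under independence.** For 80% against 96%, ψ = 0.96×0.2 + 0.04×0.8 = 0.224. The formula gives (1.386 − 0.778)/0.445 = 1.36, power about 91%. For 80% against 95%, ψ = 0.23 and power is about 87%. So 90% needs a gap of about 16 points.

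**If non-response is the positive class (n = 25).** Over ψ = 0.10 to 0.26, power is 47% down to 25% by the formula, 46% down to 24% uncorrected, 20–24% by mid-p and 10–13% by the exact test.

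**The case against.** The strongest reply is that 90% is attainable. The plan names no McNemar variant, and the uncorrected test holds its size (about 5.0% at ψ = 0.10, against about 1.9% for the exact test). It has 98% power under complete nesting and 92% at ψ = 0.11; mid-p has 95% at 0.10. With 80 responders, the top of the plan's expected range, the exact test reaches 91% at 0.10. This stands. A reader of the formula alone might infer that no discordance value gives 90%, or that 88% is a ceiling; the enumeration shows that neither is so. It does not rescue an unqualified 90%: at ψ = 0.12, with less than one man in 75 expected to be right on MRI and wrong on PET, the uncorrected test is already at 87.7%. The protocol's own background (section 2.1) makes such nesting hard to take for granted. It reports 5–10% of primary lesions as PSMA-negative and GRPr increased in 45–100% of cancers, and a tumour with no baseline uptake has no uptake change to read.

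Second, the discordance is unknown, so the low figures are conditional too. This also stands. Independence is an assumption and not a bound, and 52% should not be read as the trial's power.

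Third, the McNemar test is not expressly limited to responders, so all 100 men might enter. Granting the full 10-point gap, the formula then gives 90% only up to about ψ = 0.12, with 77% at 0.18 and 63% at 0.26. Granting it is generous: with specificity held at 90% for both modalities, the gap in overall accuracy would be 0.75×10 = 7.5 points.

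Fourth, the endpoints in sections 2.5 and 10.3 are counts of participants with an obtainable assessment, and logistic regression is also a primary Aim 2 analysis. Both are true. They limit what hangs on this number but do not make it correct.

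A reader might also want to quantify the further loss from estimating the 90%-specificity cut-off in about 25 non-responders. That needs a model for the scores and a choice of null, and the documents give neither, so no figure is offered.

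**Conclusion.** The stated 90% is wrong as written. It does not follow from 75 responders, one-sided 5% and 80% against 90% without an unstated assumption that almost no man is right on MRI and wrong on PET, together with an uncorrected or mid-p test. At discordance of 0.14 to 0.26, power is about 52–81% by the formula, uncorrected or mid-p test, and 45–68% by the exact test. These ranges rest on an assumed discordance and on complete data; the power paragraph makes no allowance for missing six-month scans, which would lower them.

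The positive class is a separate gap. The plan does not say that sensitivity is computed in non-responders, so the figures for 25 men are conditional on that reading and are not a finding about the trial.

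**What to change.** Replace the part of the sentence on the difference in sensitivities with:

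> With ~75 responders, the one-sided 5% McNemar test of 80% v 90% sensitivity has about 52% power if PET and MRI errors are independent, about 66% at 18% discordance, and about 88% (standard formula) under complete nesting; 90% power needs near-complete nesting, or a difference of about 16 points under independence.

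Alongside it:
- State the assumed discordance and its basis, and the McNemar variant to be used.
- State that sensitivity is computed in responders. If the sponsor intends non-responders or all men, say so and re-derive the power for that group.
- Report the paired difference in sensitivity with a confidence interval, and say that a non-significant McNemar test will not be read as no difference.

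The cost is a few sentences in section 10.2 and one interval in the analysis. No patients are added. The price is a less favourable stated power for the primary hypothesis of Aim 2.

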5. Approximately 45 to 60 minutes after the radiopharmaceutical IV administration, data acquisition will begin in the pelvic region and move toward the head. First, localizer MRI scans will be performed to define the table positions. After correct positioning of the spatial acquisition windows is ensured, the combined PET/MRI acquisition will be initiated with 3 to 5 table positions at a 2 to 4 minute acquisition time per table position. Only MR sequences required for attenuation correction of PET data will be acquired.
6. Vital signs (heart rate, blood pressure) will be recorded again at the completion of the study.
7. Participants will be contacted at 24 to 72 hours following the scan in order to capture potential occurring Adverse Events.

The above will be repeated approximately 6 months after HIFU or HDR local treatment, prior to standard of care biopsy to evaluate for residual disease in the prostate.

Objectives of the Study

Primary Objectives

- To demonstrate that ⁶⁸Ga-RM2 and ⁶⁸Ga-PSMA-11 PET/MRI can detect additional cancers over mpMRI.
- To demonstrate that ⁶⁸Ga-RM2 and ⁶⁸Ga-PSMA-11 PET/MRI can assess changes in response to treatment and predict PFS at 24 months.

Secondary Objective

- None

Endpoints

Primary Endpoints

- Number of participants with assessable additional prostate cancer lesions over mpMRI
- Number of participants with assessable pre- and post-treatment uptake in response to HIFU or HDR local therapy

Secondary Endpoint

- None

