6.3 Follow-up

Active subject participation ends after the 24 to 72 hour Safety Follow-up after the 2nd post-therapy scan. Investigators will follow subjects by chart review for 12 months post-scan to record any standard of care biopsies or imaging results. The investigators will assist with identification of lesions that can be biopsied, based on ⁶⁸Ga-RM2 and/or ⁶⁸Ga-PSMA11 PET/MRI findings.

If a subject transfers clinical care outside of Stanford Healthcare during the chart review clinical follow-up period, investigators will request permission to contact the treating physician.

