7. STUDY CALENDAR

	Pre-Study	Scan Date	24 to 72 hours Post-Scan	12 months
Informed consent	X			
Demographics	X			
Medical history	X			
⁶⁸ Ga-RM2		X ^a		
⁶⁸ Ga-PSMA11 (\geq 3 days and \leq 2 weeks)		X ^a		
Follow-up call to participant (24 to 72 hours)			X	
Chart review ^b				X

a: Subjects will undergo either ⁶⁸Ga-RM2 PET/MRI followed within 2 weeks by ⁶⁸Ga-PSMA11 PET/MRI, or ⁶⁸Ga-PSMA11 PET/MRI followed within 2 weeks by ⁶⁸Ga-RM2 PET/MRI. After the 1st scan, the 2nd scan will only occur after the follow-up with the patient for the 1st scan, and after a minimum of 3 days have elapsed. This will be repeated approximately 6 months after HDR local treatment, prior to standard of care biopsy to evaluate for residual disease in the prostate.

b: Subjects will be followed by chart review for 24 months from initial scan date. If a subject transfers clinical care from Stanford HealthCare, investigators may request records from the treating physician.

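### The 90% power claimed for a PFS hazard ratio of 2.5 does not follow from the plan's own 20% progression rate: about 15-16 events are expected by 24 months, about 41 are needed, and power is roughly 50-57%

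*Combined protocol and SAP*

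**What the plan says.** The power paragraph of Section 10.2 (Aim 2) gives the inputs: "We expect a 70-80% response rate to treatment, and 20% of responders progressing by two years". It counts about 75 responders among the 100 participants for the response analysis. For PFS it then uses "Median-change groups of ~40 each among the responders" and claims "90% power at one-sided 5% error to detect differences in PFS hazard ratios as small as 2.5". The test is a log-rank comparison of patients above and below the median change; a Cox regression on the amount of change is also planned. The paragraph gives no event count, formula, follow-up length or dropout allowance for this claim.

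The time horizon has to be taken from elsewhere:

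- Aim 2 in Section 1 says that imaging "assessment at 6-months follow-up will predict PFS at 24 months".
- The second primary objective in Section 2.5 is that imaging "can assess changes in response to treatment and predict PFS at 24 months".
- Footnote b of the Section 7 calendar states "Subjects will be followed by chart review for 24 months from initial scan date".
- Section 6.3 states "Investigators will follow subjects by chart review for 12 months post-scan".

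The status of PFS is mixed. It is in the second primary objective (Synopsis and Section 2.5). Section 10.2 labels as secondary the hypothesis that change in "uptake will predict progression-free survival (PFS) better than MRI". The endpoints in Section 2.5 and the registered outcomes in Section 10.3 count participants with an assessable scan.

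**The concern.** Power for a log-rank test is set by events, and the number of patients matters only through the events they supply. If one responder in five progresses by two years, two groups of 40 supply 16 events between them. That is few for a hazard ratio of 2.5, so a claim of 90% power needed checking.

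The PFS analysis has no other sample-size support. A reader who trusts the 90% would take a non-significant result as fairly strong evidence against a hazard ratio of 2.5. If the true power is near one half, such a result says little, and imaging change could be wrongly dismissed as a predictor of progression.

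**Working it through.** **Inputs.** Hazard ratio 2.5, one-sided 5%, 90% power, a 1:1 split at the median, 70-80 responders (about 75, or two groups of about 40) and 20% of responders progressing by two years: all from Section 10.2. The 24-month horizon comes from Sections 1, 2.5 and 7. No dropout is allowed for.

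**Events needed for the plan's 90%.**

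- Schoenfeld: 4 × (1.645 + 1.2816)² / (ln 2.5)² = 40.8, so 41.
- Freedman: (1.645 + 1.2816)² × (3.5/1.5)² = 46.6, so 47.

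To supply 40.8 events, 40.8/80 = 51% to 40.8/75 = 54% of responders would have to progress, more than 2.5 times the stated 20%.

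**Events expected by 24 months.** 0.20 × 70 = 14; 0.20 × 75 = 15; 0.20 × 80 = 16.

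**Power at those events.** Schoenfeld: Φ(½√D × ln 2.5 − 1.645). Freedman: Φ(√D × 1.5/3.5 − 1.645). Hazard ratio detectable with 90% power (Schoenfeld): exp(2 × 2.926/√D).

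| Events D | Schoenfeld | Freedman | Detectable hazard ratio |
|---|---|---|---|
| 14 | 52.8% | 48.4% | 4.78 |
| 15 | 55.2% | 50.6% | 4.53 |
| 16 | 57.4% | 52.8% | 4.32 |

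A simulated log-rank test agrees. Assuming exponential hazards, 20% overall at 24 months with a hazard ratio of 2.5 means 12.2% against 27.8% in the two halves. With censoring at 24 months and 20,000 runs, power is 50.2% with 35 per group, 51.1% with 37, 53.2% with 38 and 55.0% with 40.

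**Readings that favour the plan** (75 and 80 responders, exponential hazards, Schoenfeld power):

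| Reading | Events | Power |
|---|---|---|
| 20% is the rate in the better half only (20% vs 42.8%), 24 months | 23.5; 25.1 | 72%; 74% |
| 20% overall; everyone followed to month 84 (Sections 3.4.2 and 10.3) with uniform five-year accrual (Section 10.4), so 24-84 months each | 28.4; 30.3 | 79%; 81% |
| Both together | 40.4; 43.1 | 90%; 91% |

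**A reading that goes the other way.** Section 6.3 does not say which scan starts its 12 months. If it is the 6-month post-therapy scan, follow-up ends about 18 months after treatment. That gives 10.8, 11.6 or 12.4 events for 70, 75 or 80 responders, and power of 45%, 47% or 49%. If it means about 12 months in all, there are about 8 events and power is 36-38%.

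**Precision.** The 95% interval around an observed hazard ratio of 2.5 is 2.5 × exp(±1.96 × 2/√D): 0.91 to 6.88 with 15 events and 0.94 to 6.66 with 16.

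**The case against.** The strongest reply is that Section 10.2 prints no follow-up length for this test, so the 90% may rest on inputs left unstated. The combined reading above does reach it. So do two other routes:

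- Counting 25 non-responders who all progress gives 15 + 25 = 40 events and 89.5%.
- Following every responder for a full 84 months gives 39-42 events and 89-91%.

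None of these fits the documents. The 20% is stated for responders as a whole, and the power sentence is confined to responders. Chart review stops at 24 months or earlier. An 84-month study with five years of accrual cannot give every patient 84 months.

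A second reply is that the planned Cox regression on the continuous change uses more information than a median split. That is fair. Under added assumptions that the documents do not give (a normally distributed change score and a log-linear effect matched to a half-versus-half hazard ratio of 2.5), its simulated power is about 71-73% with 74-80 responders. This limits the miss rate quoted below to the log-rank test. It does not rescue the 90%, which is claimed for the median-change groups.

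A third is that PFS is labelled secondary in Section 10.2 and is not a registered outcome measure. That lowers the weight of the point. But PFS at 24 months remains in a primary objective, and in the title of a registered outcome in Section 10.3.

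**Conclusion.** The concern holds. At the plan's own rates and a 24-month horizon, 15-16 events are expected against about 41 needed. Power for a hazard ratio of 2.5 is roughly 50-57%, falling to 48% by Freedman's formula at the low end of 14 events. The median-split log-rank test would miss a true hazard ratio of 2.5 about 43-50% of the time, where the plan implies 10%.

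The event counts and the two formulas need only the stated inputs and an even split. The simulations and the longer or shorter follow-up figures also assume exponential hazards. Ignoring dropout favours the plan. The mismatch between about 75 responders and two groups of about 40 moves power by only about 2 points. The point should be fixed, but it does not call for a change to the design or to the order of the analyses.

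**What to change.** Restate the PFS power in Section 10.2 from expected events: about 15-16 by 24 months, roughly 50-57% power for a hazard ratio of 2.5, and 90% power only for a hazard ratio of about 4.3-4.8 (16 down to 14 events, Schoenfeld). State the follow-up assumed, and that the 20% applies to all responders. If the sponsor used other inputs, print them with the event count they imply, and make sure the follow-up sections provide for them.

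Reconcile the chart-review periods in Section 6.3 and in footnote b of Section 7, naming the scan from which each is counted. Say that PFS prediction will be reported as a hazard ratio with its confidence interval, so that a null result is not read as evidence of no prediction.

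The cost is wording only. The stated power becomes less favourable; no patients or procedures are added.
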